37 outcomes will be compared with those of transplant candidates who are evaluated for but
38 do not receive LDLT. The primary objective concerns comparison of morbidity and
39 mortality of patients who receive LDLT with a group or groups of patients with similar
40 illnesses and prognoses. It is also important to compare the outcomes after LDLT to
41 those after cadaveric transplantation. Transplant physicians need this information on
42 outcomes to advise patients and prospective donors. Therefore, sufficient patient and
43 donor pairs will be recruited to determine whether recipients of LDLT have substantially
44 different survival than non-LDLT recipients. A large number of donors and recipients

45 from several geographically distributed institutions will be necessary to reliably
46 determine if outcomes are different with the two approaches.

47
48 These issues are best addressed through prospective data collection. But, the main
49 outcomes of the A2ALL prospective data collection will not be available for at least 5
50 years. Therefore, to gain initial insights into outcomes associated with these procedures,
51 a retrospective cohort or look back study has been designed to compare the outcomes of
52 LDLT and cadaveric liver transplants and the outcomes for living liver donors beginning
53 in 1998 at the nine participating transplant centers of the A2ALL study. In order to be
54 conducted rapidly and efficiently, this study will rely exclusively on existing medical
55 records and patient materials.

56 **3. Study Objectives/Specific Aims**

57 **3.1. Overall Aim of the Retrospective Cohort Study**

58 The primary study objective is to determine whether the *decision* to undergo LDLT is
59 beneficial for the patients who choose LDLT. The principal hypothesis is that receipt of
60 a living liver allograft leads to better long term outcomes for liver transplant candidates
61 than *pursuit* of cadaveric transplant. This is a study of the decision to perform LDLT.
62 Several different patient outcomes will be considered.

63 **3.2. Comparison of mortality between LDLT and non-LDLT recipients**

64 **3.2.1. Primary Aim**

65 To compare the survival distribution from time of identification of a potential living
66 donor between those receiving an LDLT and those not receiving one.

67 **3.2.2. Secondary Aims**

68 To compare the survival of LDLT vs. cadaveric recipients from time of transplant.

- 69

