110 To ascertain which data elements collected via the OPTN data collection process can be
111 reliably employed for use in the prospective A2ALL Cohort Study.

112
113 To provide feedback to the SRTR and OPTN on the accuracy and completeness of
114 selected data elements.

115 **3.6. Retrospective Post-surgical Complications Study**

116 **3.6.1. Primary Aim**

117 To determine the rate of the major donor post-operative complications associated with
118 planned right lobe liver donation

119

120 To compare the major recipient post-operative complications after LDLT versus
121 cadaveric transplant.

122 **3.7. Retrospective Resource Utilization Study**

123 **3.7.1. Primary Aim**

124 To compare the resource utilization for patients who proceed to LDLT versus those for
125 whom living donation does not occur and thus proceed toward cadaveric transplant.

126 **4. Investigational Plan**

127 **4.1. Overall Study Design**

128 Most of the specific aims require LDLT recipients and control patients who did not
129 undergo LDLT. However, the identification of these controls and study start time (time
130 0) for following LDLT patients and controls will differ for the various objectives. All, or
131 nearly all, of the LDLT recipients will be included in all analyses, which will simplify
132 chart review. Many of the control patients will also be included in several analyses.
133 LDLT donors will be evaluated for surgical complications.

134

135 For the primary survival and resource utilization objectives, the study entry point is at
136 initial evaluation of a potential living donor that includes history and physical
137 examination at the transplant center. The overall design of the retrospective cohort study
138 is predicated on this definition as the starting point for inclusion in the cohort. In the
139 primary analysis (see below), the mortality of LDLT patients will be compared to
140 mortality of patients who have not yet had LDLT, regardless of subsequent events
141 (cadaveric transplant, death, or removal from waitlist for any other reason). This cohort
142 will include all those evaluated for LDLT transplants from 1/1/98 until 2/28/03. Among
143 the 9 transplant centers in the A2ALL project, approximately 40% of individuals who had
144 a potential living donor identified went on to undergo LDLT, leaving 60% as controls
145 (see Feasibility Study report [Appendix A]). Based on this report, we estimate that

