178 For certain endpoints, supplementation of cadaveric controls above those identified in the
179 retrospective cohort component of the study may be necessary. Augmentation with
180 contemporaneous cadaveric controls would most likely occur for the first one to two
181 years of a program's experience. If additional patients are required, they will be
182 identified using SRTR data, frequency matching to the characteristics of recipients
183 undergoing LDLT. Potentially, a few LDLT patients could be included in this group but
184 excluded from the primary objective analysis. This situation would arise if a donor
185 evaluation occurred in 1997, resulting in LDLT in early 1998, although this comprises a
186 very small number of patients. We anticipate supplementation with no more than 100 to
187 200 transplant recipients.

188

189 The final cohort will include the LDLT donors (approximately 300).

190 **4.2. Comparison of mortality between LDLT and non-LDLT recipients**

191 **4.2.1. Study Methods**

192 The primary aim will use the cohort of subjects evaluated for LDLT. Survival from time
193 of donor evaluation will be compared among those receiving and not receiving LDLT. In
194 addition, we will compare both survival and rejection episodes for LDLT vs. cadaveric
195 recipients from time of transplant.

196

197 Primary endpoint: Time of death or last known alive.

198 Secondary endpoint: Time from transplant to rejection episode, or last known time
199 without rejection, incidence, number and severity of rejection and incidence of steroid-
200 resistant rejection during the 1st post-transplant year.

201 **4.2.2. Participant Selection**

202 The cohort will include all of the following:

203 Potential recipient listed for liver transplantation

- 204 • age \geq 18
- 205 • single organ

206

207 Potential donor evaluated with history and physical examination occurring between
208 1/1/1998 and the start date of the A2ALL-Cohort-01 Study enrollment. This date will be
209 different for each clinical site and will be determined once site initiation is completed and
210 the site is ready to begin enrollment of prospective subjects.

211 **4.2.3. Data Elements**

212 Two limitations of chart reviews must be kept in mind: Information may be missing, and
213 information may be inaccurate. Because these problems can occur systematically, results
214 can be biased. A2ALL will be circumspect about collecting information that is limited in

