215 either respect. Sample records will be examined for completeness and ease of obtaining
216 information on all data elements before formal data collection begins.

217

218 a. At listing

219 Date of listing

220 DOB, sex, ethnicity (PHS categories)

221 Reasons for transplantation (list primary and secondary diseases)

222 MELD/UNOS status/CTP score at time of listing

223

224 b. Potential Donor

225 Date of each donor evaluation

226 Information on potential donor. Data collection on donors will largely be limited to
227 clinically significant pre- and post-donation events and a small amount of operative
228 information.

229 Donor outcome information

230 Reasons for not donating for those who do not donate

- 231 - Medical or psychological for donor
 - 232 o Medical condition (liver related vs. co-morbid medical conditions)
 - 233 o Anatomical
 - 234 o Size
 - 235 o Blood type
 - 236 o Psychological
- 237 - Donor declines/changes mind
- 238 - Recipient became too sick (or too well)
- 239 - Recipient received cadaveric transplant
- 240 - Other

241 Date of decision not to donate

- 242
243 c. Pre-transplant
244 Complications (treated ascites, treated SBP, variceal bleed, other GI bleeds requiring
245 transfusion, hepatorenal, hepatopulmonary, treated encephalopathy, TIPS,
246 portopulmonary hypertension, bony fracture [yes or no for each])
247 SBP Prophylaxis (yes/no)
248 Antiviral therapy (specific to HBV and HCV)
249 Changes in MELD, CTP, OPTN/UNOS status
250 Hospitalization admission and discharge date
251 Days in ICU
252 Death
253 Dates for each of these
254
255 d. Transplantation and beyond
256 Date of transplant
257 Selected intra-operative data
258 Hospitalization dates
259 Days in ICU
260 Retransplantation
261 Baseline immunosuppression regimen (tacrolimus, cyclosporine, or non-calcineurin
262 antagonist based); antibody induction (yes/no)
263 Treated rejection episodes within one year of transplant:
264 1. Date of rejection (treated rejection episodes separated by less than 22 days will be
265 considered the same event for analysis purposes).
266 2. Liver biopsy (when performed): Acute rejection severity as recorded in the
267 original pathology reading (mild, moderate, severe or undetermined)
268 3. Immunosuppression at transplant and at the initiation of anti-rejection therapy
269 4. Drugs used to treat rejection

270 **4.2.4. Sample Size and Power Calculations**

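### Listing is an entry condition in 4.2.2 but is not tied to time zero, so any patient listed after the donor evaluation adds death-free time to the non-LDLT side of the initial Cox analysis

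*Protocol*

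**What the plan says.** **Time zero.** Section 4.1 sets study entry for the survival and resource-utilization objectives at the "initial evaluation of a potential living donor that includes history and physical" examination, and says that the cohort design "is predicated on this definition as the starting point for inclusion in the cohort". Sections 4.2.1 and 4.2.5 likewise count from donor evaluation. The aim in 3.2.1 is worded differently: "To compare the survival distribution from time of identification of a potential living" donor.

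**Eligibility.** Section 4.2.2 asks for a "Potential recipient listed for liver transplantation" and a "Potential donor evaluated with history and physical examination occurring between" 1/1/1998 and the site's start of prospective enrolment. It gives no order for listing and donor evaluation, and does not repeat the word 'initial'. Section 4.7.2 has the same two conditions for resource utilization, without mentioning the history and physical.

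**Analysis.** Section 4.2.5 describes two comparisons. The first, called initial and approximate, is a Cox model from donor evaluation with LDLT as a time-dependent covariate. The second, called preferred, starts at LDLT surgery and compares each recipient with controls who were alive and eligible for transplant at the same time since donor evaluation. 'Eligible' is not defined.

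**Data.** Section 4.2.3 collects the "Date of listing", the date of every donor evaluation, the "MELD/UNOS status/CTP score at time of listing", and dated later changes in those severity measures.

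**The concern.** A patient is in the cohort only if two things happened: listing and a donor evaluation. The clock starts at one of them. If listing comes second, a patient who died between the two dates is never in the data, while one who lived to be listed contributes the whole interval. No death can occur in that interval among those included.

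The interval comes before LDLT (assuming LDLT follows listing), so a model with time-dependent LDLT credits it to the non-LDLT side. Mortality without LDLT is then understated and LDLT looks worse than it is. For these patients the severity score at listing is also measured after time zero.

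This is more than detail that can wait for a statistical analysis plan. The Protocol itself fixes both the entry condition (4.2.2) and the time axis (4.2.5), and the two do not meet.

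**Working it through.** The Protocol gives no figure on this point to reproduce. It supplies a mortality level, group sizes and the LDLT share; the rest has to be assumed.

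**Inputs from the Protocol**
- Non-recipient one-year survival 0.83, exponential survival (4.2.4): hazard λ = −ln(0.83) = 0.186 per year.
- 300 LDLT and 500 non-recipients (4.2.4); about 40% of candidates go on to LDLT (4.1).

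**Assumed, because not stated:** the share f listed after donor evaluation, the delay L, and the follow-up T.

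**Step 1: crude death rate and survival curve.** Let a share f of the included non-LDLT patients have a fixed guaranteed-alive delay L. Per patient:
- deaths d = (1−f)(1−e^(−λT)) + f(1−e^(−λ(T−L)))
- person-years p = (1−f)(1−e^(−λT))/λ + f[L + (1−e^(−λ(T−L)))/λ]

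Example with f = 25%, L = 0.25 year, T = 1 year:
- d = 0.75×0.170 + 0.25×0.130 = 0.160
- p = 0.684 + 0.237 = 0.922
- rate = 0.160/0.922 = 0.174, which is 0.932 of the true 0.186
- apparent one-year survival = 1 − 0.160 = 0.840, against a true 0.83

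| f, L | rate ratio, T = 1 | rate ratio, T = 3 | apparent one-year survival |
|---|---|---|---|
| 10%, 1 month | 0.991 | 0.996 | 0.831 |
| 25%, 3 months | 0.932 | 0.973 | 0.840 |
| 50%, 3 months | 0.866 | 0.947 | 0.850 |
| 50%, 6 months | 0.735 | 0.896 | 0.871 |

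**Step 2: the Cox model of 4.2.5.** The Cox model is affected less than the crude rate. It compares patients at the same time since donor evaluation, and the guaranteed-alive patients only swell the early risk sets, when few have yet had LDLT.

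Simulation settings: true hazard ratio 1, λ = 0.186, censoring between 0.2 and 3.5 years, exponentially distributed delay to listing, LDLT a mean 0.35 year after eligibility, about 40% receiving LDLT, very large samples.

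| f, mean delay | HR, clock from donor evaluation | HR, entry at listing |
|---|---|---|
| 10%, 1 month | about 1.00 | about 1.00 |
| 25%, 3 months | about 1.03 | about 1.00 |
| 50%, 3 months | 1.05 to 1.06 | about 1.00 |

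The result depends on the shape of the delay. With a fixed rather than exponential delay, three years of follow-up and the lower hazard −ln(0.875) = 0.134, the same three rows give 1.00, 1.01 and 1.01. A 50% share with a six-month delay gives 1.05 if the delay is fixed and about 1.1 if it is exponential. Nothing in the Protocol points to delays that long.

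**Step 3: scale.** With 800 patients the standard error of the log hazard ratio is about 0.145. At the upper end, ln(1.06) = 0.058, and 0.058/0.145 = 0.40 of a standard error. The effect targeted in 4.2.4 is ln(0.875)/ln(0.83) = 0.134/0.186 = 0.72. If the bias multiplied it, 0.72 × 1.06 = 0.76.

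**The case against.** **Late listing may hardly occur.** This is the strongest reply. Section 4.1 counts removal from the waitlist among events after entry; 4.5.2 and 4.6.2 speak of waitlisted patients whose donors were considered; Appendix A sorts every candidate into transplanted, died or removed, or still waiting, with no unlisted category. All this suggests that most patients were on the list at entry. It stands as a reason to expect a small effect. It does not supply the missing rule: a site applying 4.2.2 as written would include a patient listed afterwards.

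**The preferred analysis is the matched one.** That is correct, and a reader might wrongly infer that the primary result as a whole is biased. Matched controls must be eligible at the matched time, which removes the interval if eligible means listed. The effect is therefore confined to the initial Cox model and to curves from donor evaluation, provided that the term is defined in that way.

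**Later donors.** A reader might infer from 4.2.2 alone that a patient whose first donor was examined before 1998 enters through a later donor while the clock runs from the earlier one. The rest of the Protocol does not support this. Section 4.1 ties inclusion to the initial evaluation, 4.2.5 adjusts for the year of initial evaluation, and the note heading 4.5 classifies by the first donor evaluated. Section 4.1 also allows LDLT patients to be left out of the primary analysis where a donor "evaluation occurred in 1997, resulting in LDLT in early 1998, although this comprises a" very small number of patients. What remains is a missing word in 4.2.2.

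**Identification as the clock.** A reader might infer from 3.2.1 that the time from identifying a donor to examining that donor is also counted. No planned survival model starts there, and 4.2.3 lists no identification date. This is loose wording in an aim.

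**Severity timing.** Section 4.2.5 adjusts for severity without fixing it at listing, and dated changes are collected. The listing score is a problem only if it is used for patients listed late.

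**Conclusion.** The gap is real and narrow. Listing is required but not tied to time zero, and the initial Cox analysis has no delayed entry. Any late-listed patients would bias its hazard ratio, and survival curves from donor evaluation, against LDLT.

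The size is about 1.00 to 1.06 on a true hazard ratio of 1, for 10% to 50% listed late by a mean of 1 to 3 months. That is at most about 0.4 of a standard error at the planned sample size. The shares and delays are assumptions, and the Protocol does not say that late listing happened at all. The direction is fixed, and entry at listing removes the bias in every scenario tried. The matched analysis is safe on condition that eligible means listed. The correction is worth making because it is nearly free, not because the bias is large.

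**What to change.** 1. In 4.2.5, start risk time at the later of the listing date and the initial donor history and physical. Equivalently, keep donor evaluation as the time origin and bring late-listed patients into the risk set at listing. Use the same entry date for survival curves and for the resource-utilization comparison in 4.7.
2. In the matched analysis, define 'eligible' as listed at the matched time.
3. For patients listed late, take severity from the dated MELD, CTP and status values at that entry date.
4. As consistency edits only: insert 'initial' before the donor evaluation in 4.2.2 and 4.7.2, and replace 'identification' in 3.2.1 with initial donor evaluation.

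Cost: a few lines of wording and one derived date from dates already collected in 4.2.3. No extra charts are needed. The downside is that a little pre-listing follow-up is dropped. Tabulating the number listed after the initial evaluation, and by how long, would show whether the point mattered in practice.

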70 To compare rejection episodes between LDLT and cadaveric transplant recipients.
- 71 1. To determine the incidence and severity of rejection episodes occurring within
72 one year after transplantation in recipients undergoing LDLT.
 - 73 2. To determine the incidence of steroid resistant rejection
 - 74 3. To determine the incidence of recurrent rejection occurring within 1 year after
75 transplantation

76 **3.3. Retrospective Hepatitis C Virus (HCV) Study**

77 **3.3.1. Primary Aim**

78 To determine if recurrent HCV disease at 1 yr (\pm 3 months), as observed histologically, is
79 more severe in patients undergoing LDLT as compared to cadaveric transplant.

80 **3.3.2. Secondary Aims**

81 To compare the rate of fibrosis progression (comparison of 1 yr. and most recent biopsy)
82 in LDLT and cadaveric transplant

83
84 To determine if cholestatic hepatitis in transplanted patients with HCV occurs at a higher
85 rate following LDLT as compared to cadaveric transplant controls.

86
87 To determine if rejection requiring treatment occurs at a higher rate in HCV patients who
88 undergo LDLT as compared to cadaveric transplant and to correlate this frequency of
89 treatment of rejection to aggressive recurrence of HCV as defined histologically.

90
91 To compare rate of graft loss secondary to HCV between LDLT recipients and cadaveric
92 recipients.

93 **3.4. Retrospective Hepatocellular Carcinoma (HCC) Study**

94 **3.4.1. Primary Aim**

95 To compare the outcomes for patients with HCC from the time of LDLT donor
96 evaluation for those receiving LDLT versus those not receiving LDLT. Outcomes
97 considered will include survival, hospitalizations, ablative treatments, and HCC
98 status/recurrence.

99 **3.4.2. Secondary Aim**

100 To compare the demographic characteristics, HCC stage, and outcome (patient survival
101 and cancer-free patient survival) in patients receiving LDLT or cadaveric transplant with
102 HCC as either a primary or secondary pre-transplant diagnosis (excluding incidental
103 tumors discovered at the time of transplant).

104 **3.5. SRTR Data Validation Study**

105 **3.5.1. Primary Aim**

106 To estimate the completeness and correctness of selected data elements submitted by the
107 transplant centers to the Organ Procurement and Transplantation Network (OPTN) and
108 subsequently transmitted to the Scientific Registry of Transplant Recipients (SRTR).

109 **3.5.2. Secondary Aims**

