302 evaluated for LDLT, and were alive and eligible for transplant at the same time following
303 donor evaluation as the LDLT patient was when they received their transplant. This
304 analysis will involve a different set of controls for each patient, with many control
305 patients re-used in several control sets. A modified Cox regression will be performed,
306 with statistical adjustment for the re-use of controls. In both Cox analyses, variables will
307 be checked to ensure that the proportional hazards assumption is met. If non-proportional
308 hazards are detected, particularly for the LDLT effect, they will be modeled using time-
309 dependent covariates. Interactions between covariates and the LDLT effect will be
310 tested.

311
312 Survival from date of surgery for LDLT versus cadaveric transplant will also be
313 compared using Cox regression, adjusted for prognostic variables. The distributions of
314 time from transplant to rejection episode between LDLT and cadaveric transplant will be
315 similarly compared.

316
317 We will also analyze the incidence, timing, and diagnosis (biopsy-proven or not) of
318 clinically evident liver transplant rejection requiring treatment. Analyses of rejection will
319 include subsets restricted to biopsy-proven and steroid-resistant rejection episodes.

320 **4.3. Study of Hepatitis C Virus Infection**

321 **4.3.1. Study Methods**

322
323 LDLT recipients transplanted for HCV will be compared to an approximately equal
324 number of contemporaneous cadaveric controls selected from SRTR based on a diagnosis
325 of HCV. If SRTR data are not complete for HCV identification, identification of HCV
326 patients at the facility level may be required.

327 (Note: Post-transplant biopsies will be re-read by the local pathologist for grade, stage,
328 and other characteristics of recurrent HCV. The biopsy performed closest to the one-year
329 anniversary of transplant (+/- 3 months) will be employed for histologic scoring)

330

331 Primary end-point

332

333 a) Severity of disease based upon Knodell (necroinflammatory) and Ishak
334 (fibrosis) scores on liver biopsy at 1 year (\pm 3 months) post-transplant in LDLT
335 and cadaveric transplant.

336

337 Secondary end-points

338

339 a) Rate of fibrosis progression (comparison of 0, 1 year and most recent biopsy
340 [the latter must be a minimum of 12 months after the 1-year biopsy] in LDLT
341 and cadaveric transplants)

342 b) Proportion with cholestatic hepatitis

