392 re-transplant)
393
394 ALT levels (liver panel) within one month of transplant and at 1,3,6,9 and 12 months post
395 transplant.
396 Antiviral treatment (start and stop dates, specific drugs and doses used and response
397 [ETR, SVR])
398
399 Pre-transplant and post transplant treatment in both groups
400
401 HLA matching with donor
402
403 Pathology interpretation: Re-review by local pathologist and scoring using Knodell
404 (necroinflammatory) and Ishak (fibrosis) scores.
405
406 Working definition of cholestatic hepatitis:
407 1. Bilirubin \geq 4 mg/dl x 2 wks minimum, at least 8 weeks post-transplant, PLUS .
408 2. Pathology features of
409 (i) cholestasis
410 (ii) lobular or portal inflammation
411 (iii) absence of features of acute rejection and chronic rejection. PLUS
412 3. Absence of the following:
413 • hepatic artery thrombosis
414 • biliary stricture
415 • sepsis

416 **4.3.4. Sample Size and Power Calculations**

417 Primary endpoint: Comparison of Knodell (necroinflammatory) and Ishak (fibrosis)
418 scores in LDLT or cadaveric transplant at 1 year post-transplant. Predictors of disease
419 severity will be investigated using ordinal logistic regression analysis. We anticipate
420 having at least 300 LDLT recipients and 250 cadaveric recipients, but only about 1/3 of
421 these will have HCV prior to transplant. We assume sample sizes of 100 LDLT and 83
422 cadaveric recipients with prior HCV. Because sample size calculations for ordinal
423 logistic regression are difficult, we base power calculations on a two-sample t-test (2-
424 sided, $\alpha=0.05$). For fibrosis score (0 to 6) as an outcome variable, we have 91%
425 power to detect a difference of 0.5 in fibrosis score between LDLT and cadaveric
426 recipients, assuming a standard deviation of 1.0.

427
428 Secondary endpoints: To compare rate of fibrosis in LDLT and cadaveric transplants
429 (use last available biopsy). All biopsies scored for fibrosis using Ishak (0-6) and rate is
430 based on time between transplant and last available biopsy. For the presence of severe
431 histologic fibrosis at 1 year, we expect approximately 10% overall with bridging fibrosis
432 (Ishak \geq 3). We will have 83% power to detect proportions as different as 0.05 for
433 cadaveric transplant and 0.20 for LDLT, based on a chi-square test of equality of
434 proportions with $\alpha=0.05$.

435
436 We consider the power for comparing time to graft loss due to HCV based on a logrank

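### The HCV primary histology scores come from a new local re-read, and the protocol does not require the reader to be masked to graft type

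*Protocol*

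**What the plan says.** Section 3.3.1 asks whether recurrent HCV disease at one year is "more severe in patients undergoing LDLT as compared to cadaveric transplant". Section 4.3.1 defines the primary endpoint: "a) Severity of disease based upon Knodell (necroinflammatory) and Ishak" (fibrosis) scores on the biopsy at one year, plus or minus three months.

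Two places say who produces the scores. Section 4.3.1: "Note: Post-transplant biopsies will be re-read by the local pathologist for grade, stage" and other features of recurrent HCV. Section 4.3.3: "Pathology interpretation: Re-review by local pathologist and scoring using Knodell" and Ishak scores. Both describe a fresh reading made for this study. Neither mentions concealing graft type, the original report, the clinical course or the biopsy date, and neither calls for a central or second reader.

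Three neighbouring provisions bear on the point:
- Section 4.3.2 plans adjustment for center and time of transplant.
- Sections 5.1.4 and 7.2 provide for coded data sets, which concern the people analysing the data and not the person at the microscope.
- Section 4.3.4 gives the power statement for fibrosis: 91% "power to detect a difference of 0.5 in fibrosis score between LDLT and cadaveric" "recipients, assuming a standard deviation of 1.0", with 100 LDLT and 83 cadaveric recipients and a two-sided t-test at 0.05.

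**The concern.** Ishak stage and Knodell grade are semi-quantitative, and the choice between adjacent stages is partly judgment. Section 4.3.4 expects only about 10% of patients to reach Ishak 3 or more at one year, so most calls will lie among the low stages.

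The scores are made after the question has been written down, by a pathologist at the center that did the transplant. If that reader knows the graft type and leans even slightly by it, the lean goes straight into the LDLT coefficient. No covariate can separate it from a real effect, and it cannot be repaired once the slides have been scored. The same re-read may also feed the fibrosis-progression and severe-fibrosis comparisons.

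The protocol handles comparable risks differently elsewhere. In Section 4.2.3 rejection severity is taken from the original pathology reading. In Section 4.5.1 coordinators are told not to consult the earlier registry forms, and the risk that they merely confirm earlier data is discussed. The HCV re-read has no comparable instruction.

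**Working it through.** **Inputs.** From Section 4.3.4: n1 = 100, n2 = 83, SD = 1.0, target difference 0.5, two-sided alpha 0.05. From Section 4.1: nine centers. Assumed, because the protocol gives no figure: an average graft-type scoring shift b, taken over the range 0 to 0.3 Ishak points.

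**The plan's own figure.**
- Standard error: SE = SD × √(1/n1 + 1/n2) = √(1/100 + 1/83) = 0.1485.
- Degrees of freedom: 100 + 83 − 2 = 181.
- Noncentrality for 0.5: 0.5 / 0.1485 = 3.37.
- Power from the noncentral t: 91.8% (normal approximation 92.0%). The stated 91% is reproduced to within rounding.
- Smallest observed difference that is significant: critical t × SE = 0.293 Ishak points.

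**Why center adjustment does not help.** Write the score as center effect + (δ + b) × graft type + error, where δ is the true difference and b the reader's lean. The center term absorbs a reader who is strict or lenient with everyone. It leaves δ + b as one coefficient, so b is not identifiable from the data.

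**What a shift would do.** Put δ + b in place of the difference in the noncentral t. With a shift toward LDLT and no true difference, the quantity is b. With a true difference of 0.5 and a shift toward the null, it is 0.5 − b.

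| Assumed b | b / SE | Chance of significance, no true difference | Power for a true 0.5, shift toward the null |
|---|---|---|---|
| 0 | 0 | 5% | 92% |
| 0.1 | 0.67 | 10% | 76% |
| 0.2 | 1.35 | 27% | 52% |
| 0.3 | 2.02 | 52% | 27% |

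To give the shifts a concrete meaning: if one LDLT biopsy in ten is scored one stage higher than it would be under masking, and nothing else changes, b = 0.1. One in five gives 0.2, and three in ten gives 0.3. A shift of 0.2 is 0.2 / 0.5 = 40% of the difference the study is powered for.

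**Workload of masking.** 183 patients / 9 centers = about 20 one-year slides per center on average. The spread is wide: Appendix A lists 19 LDLT recipients at the smallest center and 75 at the largest. At the one-third HCV share of Section 4.3.4 that is about 6 and 25 LDLT cases.

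**The case against.** The strongest reply is that the protocol is silent on masking. It does not say that readers are unmasked. Section 8 refers to a Manual of Operations with data entry instructions, data element definitions and a code list, and slide handling could be set out there. This stands as a limit on the claim: a reader might infer that the plan prescribes an unmasked reading, and the text does not say so. It does not remove the point. The protocol names the reader twice and allows an unmasked reading, and masking is study conduct that cannot be added at the analysis stage.

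Second, nothing in the protocol says that the pathologist has the patient's file or knows the graft type. Chart abstraction and data entry are coordinators' work (Sections 4.5.1 and 7.2). That knowledge is plausible for a center's own pathologist, but it is an inference.

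Third, expectations need not all run one way. Section 3.3.1 is worded as an open question about greater severity after LDLT and the test is two-sided. Section 3.1 expects better long-term outcomes with LDLT, and Section 4.1 cites reports of less rejection. A common lean across nine centers is therefore one scenario among several, and opposing leans could partly cancel.

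Fourth, the t-test serves only for sample size. Section 4.3.5 plans ordinal logistic regression with ordinary regression in support, and Section 4.3.2 adds center and time adjustment, so the percentages would not carry over exactly.

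A reader might also infer that reader expectation could by itself create or hide the whole half-stage difference. That would need an average shift of 0.5, for example half of all LDLT biopsies raised by one stage with no cadaveric biopsy raised. Nothing in the protocol suggests a bias of that size.

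**Conclusion.** The point holds in a limited form. The primary HCV scores depend on a study-specific local re-read for which the protocol states no masking to graft type, and none of its stated safeguards removes a within-center lean. Modest assumed shifts would matter: at 0.2 Ishak points the false-positive risk is 27% rather than 5%, or power falls from about 92% to 52%, depending on direction. These figures illustrate sensitivity; they do not estimate actual bias. They rest on an assumed shift that is the same on average across centers, on the plan's SD of 1.0, and on the t-test used for planning.

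The weakness concerns the HCV study's primary endpoint and results built on the same readings. The overall survival comparison in Section 3.2 does not depend on slide reading. The stated sample size and power need no correction. Masking is worth specifying because it is cheap and works only if it is in place before the slides are read.

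**What to change.** Keep the local re-read and add to Sections 4.3.1 and 4.3.3 that:
- the coordinator selects the biopsy for the one-year window, relabels the slide with the study number and covers other labels;
- graft type, original report, clinical data and biopsy date are withheld from the reader;
- LDLT and cadaveric slides are submitted mixed, in random order, within each center;
- only scores obtained in this way enter the primary analysis.

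If the Manual of Operations already contains such a procedure, a cross-reference from these sections is enough.

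The cost is coordinator time for about 20 one-year slides per center on average, unevenly spread. It rises if the later biopsies used for fibrosis progression are masked as well. No extra reader or new biopsy is needed, and sample size, test and power are unchanged. Masking will be imperfect: a local reader may recognise some cases, most easily at a small center with only a handful of LDLT recipients.
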